**National Clinical Trial (NCT) Identified Number: NCT03861429**

**Principal Investigator: [name] NHA**

**Sponsor: University of Utah**

**Grant Number: R21AG058094**

**Funded by: NIA**

**Statistical Analysis Plan**

**August, 1, 2019**

## Randomization

We will employ a randomized wait-list control design with nursing homes and assisted living facilities. We block randomized five nursing homes and three assisted living communities in the Pacific Northwest into two groups based on size, proportion of residents with Medicaid, and proportion of residents with mild to moderate cognitive impairment. In Group 1 (early intervention group) NHs, videorecording, editing, and viewing will occur within three months of baseline. In Group 2 (delayed sharing) NHs, residents will be on a wait-list; after the delayed start, their video will be produced and viewed within three months.

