The culture-change movement that began in the 1980s in NHs is a broad effort to transform NHs from impersonal health care institutions into person-centered homes where long-term care is provided. Prior to the efforts that began three decades ago, residents often faced boredom and experienced learned helplessness, among other negative traits. The culture-change movement, however, set goals to individualize care for residents promoting person-centered care through reorientation of the facility's culture itself. Culture change strives to honor resident's individual rights, and enhances their quality of life and the quality of care that they receive. Ideally, facilities would adopt the following principles to facilitate person-centered care aligned with the culture-change movement: resident direction; homelike atmosphere; close relationships; staff empowerment; collaborative decision-making; and quality-improvement processes.

Care Conference

Care conferences are held for every resident in the NH to help the care team share information and to create a plan of care together that meets the resident's needs. A care plan includes what the resident's needs are, what the team's goals are for meeting those needs, and what steps are planned to meet the goals. Care conferences are held at least quarterly for each resident, and include the following people in the care team: the resident; family (when the resident asks them to come); nursing staff (e.g. resident care manager); social services staff; rehab staff (if applicable); activities staff; and dietary staff. In some instances

the doctor may attend. At each care conference a shared assessment is given (a list of resident needs) by the team to help create the plan of care or to revisit the goals already set. The care conference team also discusses facts about the residents, especially at the first conference, including family and work background, medical and social needs, attitude and interests, likes and dislikes. This information allows the team to create a plan (based on their completion of assigned sections of the minimum data set (MDS)). Each member knows their part, but also knows what the others are doing in the care of each resident.

End-of-Life Care Basics

“There may be no single thing that can teach us more about life than death.” – Arianna Huffington

Definition

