preferences in the videos. Including individuals with mild to moderate cognitive limitations in advance care planning discussions and expressing their EOL preferences is warranted, viable and an ethical approach.^{13,14} Incorporating Me & My Wishes into the care planning process is expected to provide an efficient and effective way for residents to communicate their care preferences for today and at EOL, and to positively influence confidence in communicating preferences and in facilitating documentation of care planning documents.

Our long-term goal is to scale and fully incorporate Me & My Wishes into multiple settings providing long term services and supports. Ultimately, integrating Me & My Wishes videos into the electronic health record or another platform allows for video viewing by multiple individuals and disciplines in various settings. Our short-term goal, and the goal of this proposal, is to conduct Stage II efficacy testing of Me & My Wishes. We will employ a randomized wait-list control design of six nursing homes (48-54 residents). Three nursing homes will be assigned to an early intervention group (residents will share videos initially) and three assigned to the wait-list controls (residents will delay sharing videos). Videos can be viewed two ways: 1) in resident quarterly care conferences; and 2) via a secured web-based link for resident-identified family members. After video viewing, the resident, family and staff can discuss key messages and preferences of the video and add to the care plan.

Specific Aim 1: Examine the efficacy of the Me & My Wishes intervention among a sample of nursing home residents with dementia.

Hypothesis 1: Compared to the waitlist control group (Group 2), the intervention group (Group 1) will have an increase in the proportion of residents with documented goals of care discussions or self-reported conversations about preferences 90 days post video viewing.

Specific Aim 2: Examine self-efficacy of communicating preferences among residents with dementia, informal (family) and formal (staff) caregivers.

Hypothesis 2: Compared to the waitlist control group (Group 2), the intervention group (Group 1) will have greater self-efficacy scores for communicating preferences 90 days post video viewing.

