Hypothesis 3: Compared to the waitlist control group (Group 2), the intervention group (Group 1), the proportion of residents with documented new or changed care planning documents (e.g. advance directive) will increase by 90 days post video viewing.

Specific Aim 3: Describe congruence of preferences observed in the Me & My Wishes video, care conference audio recording, medical record (e.g. POLST), and in family and staff surveys.

PROCEDURES

Training Checklist for Research Staff

Orientation to Project

- CITI/GCP Trainings
- Read: [name] (2015) and [name] (2017) Articles
- Review: R21 Research Plan
- Read: Training Manual Introduction
- ID Badge
- UBox
- IRB (ERIC)
- Encryption
- Skype for Business

Recruitment/Enrollment

- Review Documents: Eligibility Checklist, Demographic & Clinical Information, Consents
- Practice approaching residents and describing the study
- Practice consenting process
- Practice approaching NH staff and families to describe the study
- Practice contacting family/friends via telephone (consent and survey procedures)
- Create a Tickler System/Calendar for MMW video recording, care conference and follow ups

Video Production

- Practice facilitating the Conversation Guide
- Video Recording and Equipment
- Video Editing (see detailed process on page X)

Data Collection & Management

Cloud Storage

- REDCap: Orientation, Survey Entry and Data Management
- Data Security: Information Storage and Confidentiality
- REDCap participant tracking (enrollment, refusals, withdraws)
- Participant Tracking: IDs, Calendar, Study Enrollment

Nursing Facility (Site)

- Discuss how to perform the Chart Review
- Practice administering the Resident Surveys (baseline, time of sharing, 90 days)
- Discuss the logistics of administering the Staff and Family surveys in care conference
- Discuss how to set up Care Conference Audio Recording and Equipment
- Practice administering Staff and family surveys (baseline, time of sharing, 90 days)

Data Analysis

- Audio Transcription and verification
- REDCap – how to run reports (e.g. accrual reports)
- NVivo – (e.g. uploading documents, coding)

Chapter Three

Eligibility, Recruitment and Enrollment

Eligibility Criteria

Use the Eligibility Checklist (Appendix A) to document whether selected residents are eligible to participate in this study or not.

❖ Resident Inclusion Criteria

We will include assisted living (AL) residents in addition to nursing home (NH) residents. Inclusion criteria:

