- Identified as having Alzheimer's or related dementia (both nursing home and assisted living residents).
- BIMS 8-15 (MDS C0500; nursing home residents only);
- Makes Self Understood and Understood By Others (medical record for NH and AL);
- reside at the facility at least 2 weeks;
- identified as a long-term resident;
- age >65 years; and
- able to speak English

❖ Resident Exclusion Criteria

- Limited communication capacity (e.g. aphasia)
- Comatose state
- Severe cognitive impairment (BIMS<7; Understood by others and makes self understood > 1).

❖ Staff Inclusion Criteria

- Able to speak English
- Willing and able to watch the videos and participate in short surveys

❖ Family Inclusion Criteria

- Able to speak English
- Willing and able to watch the videos and participate in short surveys (online or in person)

Ineligible Participants

Document ineligible residents using the Eligibility Checklist and include the reason(s) for ineligibility.

Change in Participant Eligibility

Need to document if someone becomes not eligible (e.g. control group) after delayed start.

[figure not shown]
Role of the Study Coordinators:

Study Coordinators will share responsibility for participant recruitment, enrollment, and data collection. The Study Coordinators will share responsibility for data entry, management and cleaning. In addition, the Study Coordinators will work as a pair to conduct and film the Me & My Wishes videos with residents. The Study Coordinators will coordinate editing of the videos with the Video Editor and assist as needed. In addition, the Study Coordinators will share the videos with the appropriate formal and informal caregivers. Study Coordinators will complete training in study-specific recruitment, protection of the rights of human participants and confidentiality, Good Clinical Practices, and cultural competence prior to interacting with potential participants. Other responsibilities include:

- Providing a description of the study to eligible residents allowing for questions and time to consider participation.
- Describing the background of the study, including what was found in the [name] (2005) study:
 - Many times, residents aren't asked about their wishes.
 - Often, we assume that others already know what we'd want.
 - Advance Directives are narrow in focus and have not shown to guarantee that care will be provided as the resident wishes it was.
 - Advance Directives don't meet unmet needs.

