## Goals of Care

We analyzed results with an intent to treat approach using SPSS Version 24.0 (SPSS, Armonk, NY). Multilevel logistic regression (generalized estimating equations [GEE] with an autoregressive (1) working correlation matrix, logit link function) were fitted to assess the primary hypotheses. The models account for the repeated measures (3 or 4 time points), correlated, data structure per person. An additive model was conducted with contrast coding for each time point, treatment, and follow-up effects.

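### The SAP gives two goals-of-care models, and the GEE has no arm or facility-type term, so a chance setting imbalance between arms can shift its treatment and follow-up estimates

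*SAP*

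**What the plan says.** **Allocation.** The SAP (Randomization) states: "We block randomized five nursing homes and three assisted living communities in the Pacific Northwest into two groups based on size". The full list of factors reads "based on size, proportion of residents with Medicaid, and proportion of residents with mild to moderate cognitive impairment". Facility type is not on it, and the number of facilities per group is not given. The protocol (Stage II Efficacy) still describes the earlier layout, "We will employ a randomized wait-list control design of six nursing homes (48-54 residents", with three homes per group. Its Chapter Three then adds the second setting: "We will include assisted living (AL) residents in addition to nursing home (NH) residents".

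**First goals-of-care model.** The SAP's Primary & Secondary Outcomes section plans a mixed model. It names goals-of-care discussions as an outcome and has terms for arm (Group 1 vs Group 2), time and their product. The product is the effect of primary interest.

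**Second goals-of-care model.** The SAP's Goals of Care section, in the past tense, describes a logistic GEE with AR(1) working correlation, clustered on the person, used for the primary hypotheses: "An additive model was conducted with contrast coding for each time point, treatment, and follow-up effects". No arm, facility or setting term is listed.

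**Coding.** The Concordance Analysis section repeats that sentence and gives an example. Treatment equals 1 for the immediate group at Time 2 and for the wait-list group at Time 3, each at its own video sharing. Treatment is therefore a time-varying exposure and does not identify the arm.

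**Other adjustment.** Rigor and Transparency mentions a propensity score on participant characteristics. It does not name setting or say which model the score enters.

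**Setting.** One inclusion line reads "BIMS 8-15 (MDS C0500; nursing home residents only". The protocol's Care Conference text says "Care conferences are held for every resident in the NH" and does not mention assisted living.

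**The concern.** Eight facilities are the units of randomization, and they come in two kinds that may document goals-of-care discussions at different rates. With so few units, the arms can easily differ in their mix of kinds. The mixed model puts such a standing difference into its arm term. The GEE has nowhere to put it except Treatment and Follow-up. An apparent benefit or harm could then appear when the video does nothing, on the outcome and at the 90-day time point that Hypothesis 1 concerns. The two models can also give different answers, and the SAP does not say which one decides.

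**Working it through.** **1. The plan's own figure.** Inputs from Power and Sample Size: N = 48, 2 groups, m = 3 time points, correlation 0.5, alpha 0.05, f = .213. The noncentrality is f²·N·m/(1 − rho) = 0.213² × 48 × 3 / 0.5 = 13.07, with 2 and 92 degrees of freedom. Power is 0.8998, so the stated .90 reproduces. The calculation has no facility or setting component and does not bear on this point.

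**2. Possible splits.** Assume four facilities per group (not stated) and ignore the blocking. There are C(8,4) = 70 allocations. Group 1 holds 0, 1, 2 or 3 assisted living communities in 5, 30, 30 and 5 of them.
- 60 of 70 (86%): 3 nursing homes + 1 assisted living against 2 + 2. Assisted living is 25% vs 50% of facilities.
- 10 of 70 (14%): 4 + 0 against 1 + 3. Assisted living is 0% vs 75%.

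A 3:5 allocation can come closer: 1 of 3 against 2 of 5, a difference of 0.067.

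**3. What the GEE coding implies.** Taking Treatment as 0 at follow-up (the example does not say), the cell means are:

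| Time | Immediate | Wait-list |
|---|---|---|
| 1 | b0 | b0 |
| 2 | b0 + t2 + Tr | b0 + t2 |
| 3 | b0 + t3 + FU | b0 + t3 + Tr |
| 4 | – | b0 + t4 + FU |

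Seven cells and six parameters leave one constraint: equal baselines. Suppose the arms differ by a constant Δ at every time and the video has no effect. With equal arms and AR(1) weights, the fit carries ρΔ of the baseline gap forward to Time 2 and ρ²Δ to Time 3. Hence:
- Tr = Δ − ρΔ = (1 − ρ)Δ
- FU − Tr = (1 − ρ²)Δ, so FU = (1 − ρ)(2 + ρ)Δ

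| ρ | Tr / Δ | FU / Δ |
|---|---|---|
| 0 | 1.00 | 2.00 |
| 0.25 | 0.75 | 1.69 |
| 0.5 | 0.50 | 1.25 |
| 0.75 | 0.25 | 0.69 |
| 0.9 | 0.10 | 0.29 |

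If Treatment stays at 1 during follow-up, Tr is unchanged. At ρ = 0.5 the follow-up total is then 0.50 + 0.75 = 1.25, as before.

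**4. Size on the odds-ratio scale.** Assumed rates are 50% (nursing home) and 30% (assisted living), with ρ = 0.5 and equal enrolment per facility.
- Best 4:4 split: arm rates 0.75 × 50 + 0.25 × 30 = 45% and 0.5 × 50 + 0.5 × 30 = 40%. The logit difference is 0.205. Treatment OR is exp(0.5 × 0.205) = 1.11, or 0.90 if the arms are swapped. Follow-up OR is exp(1.25 × 0.205) = 1.29, or 0.77.
- Worst 4:4 split: 50% and 35%, logit difference 0.619. Treatment OR is 1.36 or 0.73. Follow-up OR is about 2.17 or 0.46.

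**5. False-positive rate.** This was simulated with no video effect: 48 residents, 6 per facility, latent within-person correlation 0.7, rates of 50% vs 30% or 60% vs 20%, and 400–500 trials per scenario. The Treatment test rejected about 7% of the time at the best split and 11–25% at the worst. With facility type in the model it rejected about 5–7%.

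**6. With an arm term.** The coding becomes seven parameters for seven cells (rank 7), so the arm effect is estimable. Tr is then the Time 2 difference minus the baseline difference, Δ − Δ = 0, and the OR is 1.00.

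**The case against.** Several points on the other side stand.

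- **The first model already handles it.** The mixed model covers the same outcome and has an arm term. On its linear scale a stable setting difference adds nothing to the interaction; only a setting difference in change over time could. It would be wrong to infer that the SAP never adjusts for arm. The leak belongs to the GEE alone.
- **Omitting the arm term can be legitimate.** Setting baselines equal is an accepted device under randomization and gains precision. Over repeated allocations the error averages out, so this is chance imbalance and not a fixed bias. With eight facilities, however, equal baselines can be far from true in the one allocation obtained.
- **The coding is partly inferred.** The Goals of Care section gives no example. The reading relies on the identical sentence in the Concordance Analysis section. That is reasonable, but it is an inference.
- **The likely split does little harm.** At the best split, about 7% false positives cannot be told apart from 5–7% after adjustment: the simulation error near 7% is about 1.2 points. Averaged over unrestricted 4:4 allocations, the rate is (60/70) × 7% + (10/70) × 11% to 25%, or 7.6% to 9.6%.
- **Evidence that the settings differ is thin.** The BIMS inclusion range is labelled as nursing-home only, but the severe-impairment exclusion carries no such label. The care-conference text is background, and its silence on assisted living shows nothing about practice there.
- **Partial protection is possible.** Medicaid share and cognitive impairment may track facility type, and the propensity score could include it. The SAP states neither.

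A reader might also infer that the facilities cannot be divided evenly, or that imbalance is certain. Eight divides 4:4. It is each type that cannot be halved under 4:4, and a 3:5 split or unequal enrolment could bring the resident mix close to balance.

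**Conclusion.** The point holds in conditional form. The SAP has two goals-of-care models that treat a standing arm difference differently, and it does not reconcile them. Facility type is neither a named blocking factor nor a term in any stated model. If goals-of-care documentation differs by setting and the arms differ in setting mix, part of that difference enters the GEE's Treatment estimate, and a larger part enters the 90-day Follow-up estimate, in either direction. Under the assumptions used, the effect on Treatment is small at the most common 4:4 split and material at the uncommon one.

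The setting rates, the correlation, four facilities per group, equal enrolment and the coding at follow-up are all assumptions. The documents do not support the stronger claim that setting differences do distort the result, or that they favour the video: they give neither the setting gap nor the split obtained.

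**What to change.** 1. Reconcile the Primary & Secondary Outcomes and Goals of Care sections into one goals-of-care model, and name the contrast that tests Hypothesis 1.
2. In the GEE models for goals of care and concordance, add an arm main effect (Group 1 vs Group 2). It removes any stable arm difference, whatever its source.
3. Add facility type as a fixed covariate. It is known for every resident. It accounts for the setting difference directly and helps if losses differ by setting.
4. Report nursing homes and assisted living communities per group, and baseline outcomes by arm.

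Changing the blocking factors is not proposed, because the SAP describes the facilities as already randomized.

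The cost is a few sentences, two degrees of freedom and some precision. With complete data and equal arms, the variance of Treatment is proportional to 1 − ρ² without the arm term and to 2(1 − ρ) with it, a ratio of 2/(1 + ρ). At ρ = 0.5 that is 1.33, a standard error about 15% larger; the penalty shrinks as ρ rises. Neither term removes a setting difference in change over time or in response to the video.

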## Primary & Secondary Outcomes

We will calculate summary statistics for baseline demographics by intervention group, to assess comparability of groups and validate randomization scheme. We will use mixed modeling to compare the outcome measures goals of care discussions and self-efficacy of communicating preferences between Group 1 (early intervention) and Group 2 (wait-list) at 3 time points. Our specific model will be:  $Y = B_0 + B_1X + B_2T + B_3(X \cdot T) + e$  where, Y= goals of care discussions or self-efficacy of communicating preferences, X = Treatment condition (Group 1 vs. Group 2), T = Time point (baseline, 3 months, 6 months). Evaluation of the fixed effect of Treatment condition will tell us whether the two groups differ on average across all time points. The fixed effect of Time will tell us whether goals of care discussions change over time. Evaluation of the interaction of Treatment by Time will tell us if the groups change differentially, and will be the effect of primary interest.

## Rigor and Transparency

To address rigor, we will explore missing data patterns in SPSS using the Missing Value Analysis tool. We will specify the pattern fixed effects and interactions utilizing Little's test for Missing Completely at Random. Systematic missingness (as determined by missing data patterns) may be included in our mixed effects model. To increase rigor, we will employ a propensity matching score on participant characteristics (e.g. dementia type) to help reduce any treatment vs. control confounding bias.

## Power and Sample Size

Sensitivity analysis was conducted with G-Power 3.1. With a proposed sample size = 48, 2 Groups, 3 timepoints, correlation between time points = .5, power = .90, and alpha = .05, we will be able to detect a medium effect size  $f = .213$  using a general linear modeling of repeated measures looking for within-between subjects' interaction. T= Time point (baseline, 3 months, 6 months).

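### The SAP's power of .90 at f = .213 treats 48 residents as independently allocated, although whole facilities were randomized and no facility count, cluster size or intra-facility correlation enters the calculation

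*SAP*

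**What the plan says.** The SAP's Power and Sample Size section reports a sensitivity calculation: "Sensitivity analysis was conducted with G-Power 3.1". Its inputs are "With a proposed sample size = 48, 2 Groups, 3 timepoints, correlation between time points = .5, power = .90, and alpha = .05". The result is a detectable effect of f = .213 for the within-between interaction of a repeated-measures general linear model. That matches the target in Primary & Secondary Outcomes: "Evaluation of the interaction of Treatment by Time will tell us if the groups change differentially, and will be the effect of primary interest".

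The unit of allocation is the facility. The SAP's Randomization section says "We block randomized five nursing homes and three assisted living communities in the Pacific Northwest into two groups". The protocol (Chapter Two, Stage II Efficacy) says "We will employ a randomized wait-list control design of six nursing homes (48-54 residents", with three homes per group. Its Participant Confidentiality section in Chapter Three also says that study sites are what is assigned at random. Neither document describes allocation of individual residents.

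No facility count, number of residents per facility, intra-facility correlation or design effect appears among the power inputs or elsewhere. The model equation in Primary & Secondary Outcomes has no facility term. Goals of Care and Concordance Analysis account for correlation within a person only. The propensity score in Rigor and Transparency uses participant characteristics and does not deal with clustering.

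**The concern.** When facilities are randomized, the group-by-time effect is estimated from differences between a handful of facilities. Two things then separate the design from the calculation. First, a test built on the randomized unit has far fewer error degrees of freedom. Second, if residents of one facility tend to change together, 48 residents carry less information than 48 independent people.

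Changing together is plausible here. Residents of a facility share a site champion, and the videos are shown and discussed at care conferences run by the facility's own staff.

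A constant difference in level between facilities does not matter for this effect, because it cancels from the group-by-time contrast. The relevant quantity is the facility-by-time component, that is, the correlation of change among residents of one facility.

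At stake is the meaning of the stated power. A reader would take 90% power at f = .213 as a property of the trial, when it depends on an unstated assumption. The point is also separate from how the analysis models treat facility. Adding a facility term would leave the printed figure unchanged, and the amended analysis would generally have less power than the SAP states.

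**Working it through.** **Inputs from the SAP (Power and Sample Size).** N = 48, k = 2 groups, m = 3 time points, correlation rho = .5, alpha = .05, f = .213, stated power .90.

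**Inputs from the SAP (Randomization).** 5 + 3 = 8 facilities. The protocol has 6.

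**Assumptions.** Equal facility sizes (48/8 = 6 residents, or 48/6 = 8), equal numbers of facilities per arm, sphericity, no dropout. The ICC of change is not given in the documents, so 0, .01, .05 and .10 are shown.

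**Step 1: reproduce the SAP's figure.**

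- Noncentrality: lambda = f² × N × m / (1 − rho) = .213² × 48 × 3 / .5 = 13.07.
- Numerator df = (k − 1)(m − 1) = 2.
- Error df = (N − k)(m − 1) = 46 × 2 = 92.
- Power from the noncentral F(2, 92) is .8998. Solving for f at power .90 gives .2131.

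The match identifies the routine. Its 92 error df count each resident as a separately allocated unit.

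**Step 2: use facility-level error df.** With F facilities the error df are (F − 2)(m − 1): 6 × 2 = 12 for eight, 4 × 2 = 8 for six. At zero correlation of change lambda stays at 13.07.

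- Eight facilities, F(2, 12): power .818. The f needed for .90 is .239.
- Six facilities, F(2, 8): power .760. The f needed for .90 is .257.

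A simulation of the eight-facility case (20,000 runs, zero correlation of change) gave .814 for a 4 v 4 split and .79 for 3 v 5. The SAP does not state the split.

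**Step 3: allow correlated change.** Divide lambda by DE = 1 + (M − 1) × ICC, where M is residents per facility. The detectable f grows by the square root of DE; for eight facilities at ICC .05, .2392 × √1.25 = .267.

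| ICC of change (assumed) | DE, 8 × 6 | Power, F(2, 12) | Detectable f at .90 | Power, DE only, 92 df | Power, 6 × 8, F(2, 8) |
|---|---|---|---|---|---|
| 0 | 1.00 | .818 | .239 | .900 | .760 |
| .01 | 1.05 | .798 | .245 | .884 | .731 |
| .05 | 1.25 | .722 | .267 | .820 | .625 |
| .10 | 1.50 | .638 | .293 | .742 | .523 |

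The fifth column separates the two sources of loss. Even with all 92 df kept, the design effect alone lowers power to .88, .82 and .74.

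**Step 4: scale of the effect.** If the groups differ at one follow-up only, by delta SDs, then f = delta / √18. So f = .213 is .213 × 4.243 = 0.90 SD, f = .239 is 1.01 SD and f = .293 is 1.24 SD.

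**Step 5: other sample size.** With the protocol's upper figure of 54 residents in eight facilities and zero correlation of change, lambda = .213² × 54 × 3 / .5 = 14.70, and power with F(2, 12) is .86.

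**The case against.** The strongest reply is that at zero correlation of change the SAP's figure is right. Residents' changes are then independent, and a resident-level test holds its type I error (.050 by simulation) and has .90 power. This stands. A reader might infer from Step 2 that the design cannot exceed .82 even without any intra-facility correlation. The documents do not support that. The .82 belongs to a test with facility-level error df, 48 residents and an even 4 v 4 split. It is .86 with 54 residents and .79 with a 3 v 5 split, so it is one scenario and not a ceiling.

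What does not stand is using that case to defend the printed figure. The SAP never says that it assumes zero correlation of change, and gives no reason to expect it. If the assumption fails, the resident-level test no longer holds its size: by simulation its type I error is about .06 at an ICC of .01 and .09 at .05.

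Three further objections have some force.

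- Every value at a nonzero ICC is illustrative. True; they should be read as a range and not as a forecast.
- The Goals of Care section describes a logistic GEE with additive contrasts over three or four time points, which is not the test recalculated here. True, but the SAP's power statement is itself tied to a continuous repeated-measures interaction, and the recalculation stays with that test.
- The later SAP sections are in the past tense, so restating planned power may change no decision. That limits the consequence to interpretation. The documents contain no rule that a null result excludes f = .213, so that misuse cannot be attributed to the plan.

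**Conclusion.** The concern holds as an omitted design feature. It is not an arithmetic error: the calculation is correct for 48 independently allocated residents, and the trial did not allocate residents.

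Power of .90 at f = .213 requires both a zero facility-by-time correlation and a resident-level test. Under facility-level error df with eight equal facilities split 4 v 4, the shortfall is about 8 percentage points at zero correlation of change (.90 to .82) and about 26 at an assumed ICC of .10 (.90 to .64). With the protocol's six homes the corresponding values are .76 and .52. That the calculation ignores clustering rests on the documents alone. The size of the loss depends on the choice of test, the facility split and an ICC that the documents do not give.

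**What to change.** In the SAP's Power and Sample Size section, keep N = 48 and make three changes.

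1. Say that .90 at f = .213 assumes independent residents, as under individual randomization.
2. State the number of facilities actually randomized, their split between the groups and the residents per facility, and reconcile the SAP's eight with the protocol's six.
3. Restate power at f = .213, and the f detectable at .90, with facility-level error df over a range of ICCs of change marked as assumptions. For eight facilities split 4 v 4 with six residents each, that would read: power about .82, .80, .72 and .64, and detectable f about .24, .25, .27 and .29, at ICCs of 0, .01, .05 and .10.

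The cost is a short recalculation and a few sentences. No residents or facilities are added. The stated power becomes less favourable.
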